6.8.2. Prohibited Medications

Medications prohibited between Screening and Wk 12 are as follows owing to their potential to confound safety (and efficacy) assessments.

- Topical corticosteroids, topical calcineurin inhibitors, topical PDE4 inhibitors
- Oral immunosuppressants
- IV corticosteroids or biological immunosuppressants
- Phototherapy

If a participant requires a prohibited medication to address an urgent clinical need (e.g. extremely active disease, see Section 7.1.4) this should be recorded as a protocol deviation. The protocol deviation may affect the evaluability of the participant and should be discussed with the Medical Monitor in advance, if possible.

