1.1. Objectives, Estimands and Endpoints

Objectives	Endpoints
Primary	
To compare the clinical effect of a single intravenous (IV) infusion of 2 mg/kg of GSK1070806 versus placebo in moderate to severe Atopic Dermatitis in the Biologic Naïve (BN) population (Group 1).	Percent change from baseline (PCFB) in the Eczema Area and Severity Index (EASI) at Week 12
Secondary	
• To further compare the clinical effect (GSK1070806 versus placebo) in the BN population (Group 1).	 Change from Baseline (CFB) in the EASI at Week 12. EASI 50/75/90 defined as ≥ 50/75/90% reduction in the EASI from Baseline at Week 12. Investigator Global Assessment (IGA) score of 0 or 1 at Week 12.
To estimate the clinical effect of GSK1070806 in the dupilumab inadequate responder (Dupi-IR) population (Group 2).	PCFB in the EASI at Week 12.
To assess safety and tolerability (GSK1070806 versus placebo) in the combined AtD population (Groups 1 and 2).	 Incidence of serious adverse events (SAEs) and adverse events (AEs). Incidence of clinically important findings in: Vital signs Electrocardiogram Laboratory: haematology, clinical chemistry and urinalysis.
To assess anti-drug antibody (ADA) formation in the combined AtD population (Groups 1 and 2).	Incidence of ADAs

Primary estimand

The primary clinical question of interest is: What is the treatment effect on Eczema Area and Severity Index (EASI) after 12 weeks of treatment with a single intravenous (IV) infusion of 2 mg/kg GSK1070806 versus placebo in Biologic Naïve participants (Group 1) with moderate to severe Atopic Dermatitis in the absence of use of Rescue Therapy.

[figure not shown]
The primary estimand is described by the following attributes:

- Population: Biologic Naïve (BN) participants with moderate to severe Atopic Dermatitis.
- Treatment condition: A single 2 mg/kg one-hour IV infusion of either GSK1070806 or placebo at Day 1.
- o Variable / endpoint: Percent change from Baseline to Week 12 in the EASI.
- o Summary measure: Difference (GSK1070806 placebo) in mean percent change from baseline in EASI at Week 12.
- o Intercurrent events: Use of Rescue Therapy. It will be handled with a hypothetical strategy, i.e. values after use of Rescue Therapy will be set to missing.

Rescue Therapy is defined in this document as the use of any prohibited medication (as defined in the protocol section 6.8.2) that is considered as an important protocol deviation.

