Rationale for estimand: The study is designed to evaluate the treatment effect attributable to GSK1070806. It is important that this effect is not confounded by the effect of other treatments. Therefore, for participants who use any Rescue Therapy, a hypothetical strategy will be used in order to estimate the treatment effect in the absence of use of Rescue Therapy.

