4.2.2. Main analytical approach

The analysis will be carried out for Group 1 only, using data up to Week 12.

The analysis will be based on the Safety analysis set. Participants will be analysed according to the treatment they received.

EASI scores collected after use of Rescue Therapy will be set to missing.

Missing observations will be assumed to be Missing at Random (MAR), i.e. assume that the missing part, given the history, will be like the data observed in the absence of Rescue Therapy.

Endpoint(s)				
 Percent Change from Baseline in the EASI at Week 12 (Group 1) (Hypothetical Strategy, robust MAP Prior) 				
Analysis Metho	d			
Bayesian repeat	ed measures model			
Model Specifica	ation			
Outcome	Percent change from baseline in the EASI			
Baseline EASI score (continuous)				
Treatment (categorical, reference: placebo)				
Predictors	 Visit (categorical, weeks 2, 4, 8, 12, reference: Week 12) 			
	Treatment*visit interaction (categorical)			
	Baseline EASI*visit interaction (continuous)			

	Baseline EASI score will be centered around its observed mean prior to inclusion in the model		
Prior distributions for parameters associated to the predictors	 Placebo at Week 12: robust MAP prior: mixture prior has 28.5% weight on a Normal (-31.56, SD=5.67), 21.5% weight on a Normal (-31.21, SD=11.00) and 50% weight on a Normal (-30, SD = 50) GSK1070806 at Week 12: vague prior Normal(-30, SD=50) All other parameters: vague priors Normal(0, SD = 106) 		
Prior distribution for residual covariance matrix	• Σ: unstructured residual covariance matrix of dimension 4×4 ~ Inverse Wishart (J, S), with J = number of visits (degree of freedom), S = identity matrix		
	If convergence issues occur, an alternative covariance matrix structure may be used, for example a compound symmetric structure, to help improve convergence.		

Model Checking & Diagnostics

See Section 4.1.1

Results Presentation

- Adjusted posterior median, and 95% Crl for each treatment by timepoint interaction (table).
- Posterior median treatment differences (GSK1070806 placebo) and associated 95% Crl for each timepoint (table and figure).
- Probabilities that the true treatment difference (GSK1070806 placebo) at each visit is < 0%, 15%, -25%, and -40% (table), e.g., Prob(GSK1070806 placebo < -15%)
- Outputs will include results for earlier timepoints in addition to the objective specified timepoint of Week 12.

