4.2.4. Additional estimands

An additional estimand for the primary endpoint is defined: the intercurrent event of the use of Rescue Therapy will be handled with the treatment policy strategy: data collected after use of Rescue Therapy will be included in the statistical analysis.

Missing data assumption will be MAR, i.e., given the history of a subject, the part that is missing will be distributed similarly as those that are still in the study at that time, whether they have taken Rescue Therapy or not.

The same statistical approach as described in Section 4.2.2 will be used.

Primary endpoint additional analysis due to COVID-19

For the primary endpoint, if >= 6 participants in Group 1 have confirmed COVID-19 up to Week 12, then an additional analysis whereby the intercurrent event of the onset of COVID-19 (confirmed diagnosis only) will be handled with the hypothetical strategy may be conducted.

EASI scores collected after the onset of COVID-19 (confirmed diagnosis only) will be set to missing.

Missing observations will be assumed to be Missing at Random (MAR), i.e. assume that the missing part, given the history, will be like the data observed in the absence of COVID-19.

For the use of Rescue Thearpy, the same method (hypthetical stratgey) as in the primary analysis will be used.

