4.3.1.2. Main analytical approach

The analyses of the secondary endpoints will be based on the Safety analysis set. Participants will be analysed according to the treatment they received.

Group 1 – continuous endpoints

The approach is the same as that used for the primary endpoint (Section 4.2.2), including up to Week 12 visit. Vague prior of Normal(0, SD=10⁶) will be used for all parameters associated to the predictors. EASI scores will be set to missing after Rescue Therapy. Missing data will be assumed to be MAR.

Group 1 – binary endpoints

Bayesian logistic regression will be used.

Responses collected after use of Rescue Theapy will be set to non-responders.

Missing responses will be imputed as non-reponders.

Binary Endpoints					
 EASI50, EASI75, and EASI90 responses at Week 12 					
 IGA score of 0 or 1 	response at Week 12				
Analysis Method					
Bayesian Logistic Regi	ression				
Model Specification					
Outcome	$y_i = Ry_i = response (0/1)$ for participant i at Week 12				
Predictors	Treatment (categorical) Baseline score (continuous) Baseline score will be centered around its observed mean prior to inclusion in the model				
Model	$y_i \sim Ber(p_i)$ $logit(p_i) = (Treatment=Placebo) \times \beta_1 + (Treatment=GSK) \times \beta_2 + (Baseline\ score) \times \beta_3$				
Prior distributions for coefficients (β)	$\beta = \text{parameters associated to predictors}$ $\bullet \beta_1, \ \beta_2 \text{: vague prior such that logit}^{-1}(\beta_k) \sim \text{Beta}(1/3, \ 1/3)$ $\bullet \beta_3 \beta_k \text{: vague prior N}(0, \ \text{SD}=10^6)$				

Model Checking & Diagnostics

See Section 4.1.1

Results Presentation

- Adjusted posterior median and 95% Crl of true response rate for each treatment group, using the back-transformation of the logit (table).
- Posterior median and 95% Crl for the true difference in proportion of responders (GSK1070806

 placebo) (table)

- Probabilities that the true treatment difference is greater than 0 and 10%.
- Outputs will include results for earlier timepoints in addition to the objective specified timepoint
 of Week 12.

Group 2 - continuous endpoint

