The PCFB in the EASI in Group 2 in the GSK1070806 arm will be analysed using a simplified version of the approach used for the primary endpoint (Section 4.2.2) with only one treatment arm. EASI scores will be set to missing after Rescue Therapy. Missing values are assumed to be Missing at Random (MAR). Vague priors of Normal(0, SD=10⁶) will be used for the parameters associated to the predictors.

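### Does the SAP need a written threshold for when prohibited medication counts as Rescue Therapy?

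*SAP*

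**What the plan says.** Rescue Therapy is the only intercurrent event in the primary estimand (SAP section 1.1). It is use of a prohibited medicine ("as defined in the protocol section 6.8.2) that is considered as an important protocol deviation". The reason given for the hypothetical strategy is: "It is important that this effect is not confounded by the effect of other treatments".

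The label acts in three places:

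- **Group 1 continuous endpoints (SAP 4.2.2 and 4.3.1.2).** EASI after Rescue Therapy is set to missing. The missing-at-random assumption is to "assume that the missing part, given the history, will be like the data observed in the absence of Rescue Therapy".
- **Group 1 binary endpoints (SAP 4.3.1.2).** "Responses collected after use of Rescue Theapy will be set to non-responders".
- **Group 2 percent change in EASI (SAP 4.3.1.2).** "EASI scores will be set to missing after Rescue Therapy".

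Protocol section 6.8.2 lists the medicines, has urgent use recorded as a deviation and adds: "The protocol deviation may affect the evaluability of the participant". It does not grade deviations. SAP section 6.1.3 includes prohibited medication among the kinds of important deviation and has the tracked deviations reviewed before unblinding and database freeze. SAP section 6.1.4 promises summaries of prohibited medications and of Rescue Therapy, overall and split into topical and non-topical use.

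On the primary endpoint, SAP section 4.2.4 goes further: "An additional estimand for the primary endpoint is defined", under which data after Rescue Therapy are kept. For the secondary efficacy endpoints, section 4.3.1.3 plans no sensitivity analysis and section 4.3.1.4 leaves the use of post-rescue data optional.

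**The concern.** An intercurrent event should be recognisable from the plan. Here one word, *important*, decides which observations are deleted, and it is left to judgement. Two readers could sort the same short course of topical steroid differently. Unlabelled use stays in the data that the model treats as free of rescue, which works against the stated aim of an unconfounded effect.

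The cases at issue are participants who take a prohibited medicine briefly and remain to Week 12. With 10 placebo participants, each decision carries weight, most of all for the binary endpoints: they have vague priors, and SAP section 4.3.1.2 will report "Probabilities that the true treatment difference is greater than 0 and 10" percent. An optional unblinded interim uses the same model as the primary analysis (SAP 4.7), and the timing of the deviation review in SAP 6.1.3 does not mention it.

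**Working it through.** **1. The passages side by side.** SAP 1.1 supplies the qualifier and SAP 6.1.3 supplies a category and a process. Together they support reading prohibited use as important by default, subject to a review done without treatment codes. Against that, the qualifier would be redundant if every use counted, and SAP 6.1.4 names the two sets separately. Some filter is needed in any case: Protocol 6.8.2 prohibits topicals from Screening, while participants need only stop them at Day -7, so a literal any-use rule would catch pre-dose use. Analysts would confine the label to use after dosing.

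**2. Cases the label does not decide.** Protocol 7.1.4 withdraws anyone who starts and continues a prohibited medicine for considerable worsening. SAP 6.2.4 does not remap early-withdrawal visits, and SAP 4.3.1.2 counts missing responses as non-response. A withdrawn participant with no Week 12 visit is therefore a non-responder whatever the label. Protocol 7.2 encourages withdrawn participants to attend later visits, so this covers some cases and not all.

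**3. The plan's own table.** Inputs from SAP section 5: placebo n = 10, active n = 20, SD 50, placebo mean -30, active prior N(-30, 50), placebo prior 0.285 N(-31.56, 5.67) + 0.215 N(-31.21, 11.00) + 0.5 N(-30, 50). For prior component j with mean m_j, SD s_j and weight w_j, and placebo mean y on n participants:

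- v_j = 1/(1/s_j² + n/50²)
- posterior mean_j = v_j (m_j/s_j² + n y/50²)
- posterior weight ∝ w_j × Normal density of y with mean m_j and variance s_j² + 50²/n

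Simulating 200,000 trials per scenario (Week 12 only, SD known), at true differences of -40, -25, -15 and 0:

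| Criterion | Stated (%) | Recomputed (%) |
|---|---|---|
| >75% that difference < -15% | 82.6, 43.9, 18.4, 2.5 | 82.7, 43.9, 18.5, 2.5 |
| >75% that difference < -7.5% | 92.8, 66.6, 37.7, 7.8 | 92.8, 66.6, 37.8, 7.6 |
| >97.5% that difference < 0% | 68.8, 30.3, 10.9, 1.0 | 68.9, 30.3, 10.9, 1.0 |

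**4. Primary endpoint, one placebo participant (assumed data).** Nine average -30. The tenth is set to missing or kept at -45, -60 or -80.

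- Raw means if kept: (9 × -30 - 45)/10 = -31.5; (9 × -30 - 60)/10 = -33.0; (9 × -30 - 80)/10 = -35.0.
- Posterior means if kept: -31.43, -32.00, -32.76. If missing: -30.87. Shifts: 0.6, 1.1 and 1.9 points.
- With the -80 value, P(difference < -15%), kept v missing: 0.541 v 0.586 at an active mean of -50, and 0.919 v 0.936 at -70.

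**5. Primary endpoint, several users (assumed data).** True difference -25, users on placebo only, each with 20 to 40 points of extra improvement. The chance of meeting the first criterion (stated 43.9%) is:

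- 2 users: 42.9% if all are labelled, 38.5% to 33.3% if none is.
- 4 users: 41.5% if all are labelled, 33.3% to 23.3% if none is.

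The none-labelled end uses the same data and model as the treatment-policy analysis, so the report will show it.

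**6. Binary endpoints (assumed data).** Posterior Beta(1/3 + x, 1/3 + n - x) in each arm, baseline covariate omitted, 4,000,000 draws. The starting case, 10/20 v 2/10, is near the 50% and 15% EASI-75 rates that Protocol 2.1 quotes for dupilumab and placebo.

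| Active, placebo | Median difference (points) | 95% CrI | P(difference > 10%) |
|---|---|---|---|
| 10/20, 2/10 | 29.0 | -6 to 57 | 0.87 |
| 10/20, 1/10 | 38.3 | 7 to 63 | 0.96 |
| 9/20, 1/10 | 33.4 | 2 to 59 | 0.93 |

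Relabelling one placebo responder moves the median by 38.3 - 29.0 = 9.3 points; one active responder moves it by 38.3 - 33.4 = 4.9. These are close to 1/10 and 1/20.

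**7. Group 2 (assumed data).** One of 15 kept, the others at -45: (14 × -45 - 60)/15 = -46.0 and (14 × -45 - 80)/15 = -47.3, so shifts of 1.0 and 2.3 points.

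**8. Would a written rule do better?** One candidate borrows the 7-day topical washout and counts topical use within 7 days before an EASI visit. EASI visits after dosing, up to Week 12, are on Days 15, 29, 57 and 85. Use on Days 30 to 49 and 58 to 77, 20 + 20 = 40 days in all, would trigger nothing, while a single application on Day 14 would set every later score to missing. The other candidate counts all use after dosing. It discards trivial use too: the third criterion at -40 falls from 68.8% to 66.8% with 9 placebo and 20 active values, and to 61.8% with 8 and 18.

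**The case for a change.** The strongest opposing case is that an estimand should be reproducible from the plan and that writing a criterion costs a few sentences. The firm treatment-policy analysis covers only the primary endpoint. In the example above, one placebo label decides whether the 95% interval includes zero, and with active at 6/20 it moves P(difference > 10%) from 0.49 to 0.74. The interim could stop the study, and the study statistics team prepares it on unblinded data (Protocol 9.5.2).

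It stands that no threshold is written and that a reader cannot reproduce each label. A sentence saying whether all post-dose use up to Week 12 counts would be a harmless courtesy. The rest is weaker. The large binary shift needs a placebo participant who responds at Week 12, has taken a prohibited medicine, and is judged unimportant by people without the codes; nothing in the documents says how likely that is. On the interim, the study team tracks the deviations, and apart from statistics, programming and clinical pharmacology modelling it has no access to the unblinded schedule. The interim charter and the output specification were not available and may settle the point. SAP 4.3.1.4 sits between figures missing from the text, so its full content is uncertain.

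**Conclusion.** No change follows. This is a gap that analysts can fill sensibly: a review without treatment codes, starting from a list that already names prohibited medication and limited to use after dosing, would give sound results. The effect on the primary result is small for one participant. It grows only if several placebo users with large extra improvement go unlabelled, and the planned treatment-policy analysis would expose that. The binary shifts of about 9 or 5 points per relabelled responder come from the arm sizes and would follow from any rule. If prohibited use and Rescue Therapy are tabulated separately, as SAP 6.1.4 suggests, a reader can see how much use was left unlabelled.

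The trial is Phase Ib with no formal hypothesis and no multiplicity adjustment, so no error rate rests on the label. The conclusion assumes that labels are settled without treatment codes, including for any interim data cut. The sizes rest on assumed outcomes, a known SD of 50, Week 12 data alone and no baseline covariate.

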1.2. Study Design

Overview of	Study Design and Key Features
	 The overall study duration for an individual participant is not expected to exceed 28 weeks (Screening is 4 weeks; Treatment Period is 12 weeks; Follow-Up Period is 12 weeks). The End of Study (Week 24, Day 169) would allow for continued safety monitoring beyond the Week 12 primary endpoint. The study will assess the impact of GSK1070806 in two groups of
	patients with moderate-to-severe AtD. Groups 1 and 2 will be conducted in parallel.
	 Group 1: Patients naïve to biologic treatment (and who have failed topical therapies).
	Group 2: Patients who have not adequately responded (or have been intolerant) to dupilumab (Dupixent).
Study interventio n	• All participants must meet all clinical criteria at the point of randomization (for subsequent dosing on Day 1) and must stop using topical treatments (corticosteroids, calcineurin inhibitors or Phosphodiesterase 4 [PDEIV] inhibitors) for at least 7 days (starting on Day -7) prior to dosing on Day 1.
	GSK1070806 and placebo are double blinded. Participants will receive either GSK1070806 or placebo on Day 1.
Study intervention	Approximately 64 patients are expected to be screened to achieve approximately 48 randomly assigned participants.
Assignment	 Group 1: N = 30. 20 participants will receive GSK1070806, 10 will receive placebo in a 2:1 ratio. Approximately 40 BN patients may need to be consented for screening to provide 30 randomized. Group 2: N = 18. 15 participants will receive GSK1070806, 3 will receive placebo in a 5:1 ratio. Approximately 24 Dupi-IR patients may need to be consented for screening to provide 18
	randomized.
Interim Analysis	The details of the planned analysis and timing will be documented in the Interim Charter. Refer to Section 4.7 for details.
Analyses	• Primary completion analysis: when the last participant in Group 1 completes the Week 12 visit or withdraws from the study prior to Week 12.

Overview of Study Design and Key Features				
• Final analysis: when the last participant completes the Week 24 vi				
	or withdraws from the study prior to Week 24			

2. STATISTICAL HYPOTHESES

There is no formal hypothesis to be tested.

2.1. Multiplicity Adjustment

There will be no adjustment for multiplicity.

3. ANALYSIS SETS

For the purposes of analysis, the following analysis sets are defined:

Analysis Set	Definition / Criteria	Analyses Evaluated
Screened	All participants who signed the ICF and are screened for eligibility.	Study Population
Enrolled	All participants in the Screened analysis set who entered the study.	Study Population
Randomised	 All participants in the Enrolled analysis set who were randomly assigned to study intervention in the study. Participants will be analysed according to the intervention they were randomized to receive. 	Study Population
Safety	 All participants in the Randomized analysis set who received the study intervention. Participants will be analysed according to the intervention they actually received. 	EfficacySafetyBiomarkerPROs
Pharmacokinetic (PK)	 All participants in the Safety analysis set who had at least 1 non-missing PK assessment (Non-quantifiable [NQ] values will be considered as non-missing values). Participants will be analysed according to the intervention they actually received. 	• PK
COVID-19	All participants in Safety analysis set who had confirmed COVID-19 diagnosis.	Safety

The term "Analysis Set" will be referred to as "Population" in the displays.

4. STATISTICAL ANALYSES

4.1. General Considerations

Unless otherwise specified, the Enrolled or Randomized Analysis Sets will be used for all Study Population analyses (detailed in the Output and Programming Specification (OPS)), the Safety Analysis Set will be used for all Efficacy, Safety, Biomarker, and PRO analyses, and PK Analysis Set will be used for PK analyses.

In the case of wrong group (i.e., Group 1 vs Group 2) assignment at the time of randomization, the analyses will be performed based on the actual group per data collected in the CRF.

Unless otherwise specified, summary tables will provide the following descriptive statistics as a minimum:

- Continuous data: n, mean, standard deviation, minimum and maximum.
- Continuous data (log-normally distributed): n, geometric mean, %CVb, minimum, maximum
- Categorical data: number and percentage of participants in each category.

4.1.1. Bayesian inference

The main statistical analyses will be carried out in the Bayesian framework. Models will be fitted by Monte Carlo Markov Chain (MCMC) simulations.

Prior distributions are given in the analysis sections below and will be reported in the Clinical Pharmacology Study Report (CPSR).

Posterior distributions for each arm and for the treatment difference between arms will be summarized using posterior median, 95% equal-tailed credible intervals (CrI), and posterior probabilities of the true treatment difference being greater than pre-specified thresholds.

The inference will be carried out as follows:

- 2 chains will be run, with different (over-dispersed) initial values in order to assess convergence. Posterior summaries will use only 1 chain.
- A minimum burn-in period of 1,000 MCMC samples (for each chain) will be used.
- A minimum of 10,000 MCMC samples (for each chain) will be run to generate samples of the posterior distribution.
- A thinning sample may be used to improve convergence. If k is the thinning ratio, the number of MCMC samples will be minimum $k \times 10,000$.

To assess convergence (MCMC), the following will be used:

- Ratio of Monte Carlo error /posterior SD should be as small as to ensure that only a fraction of the posterior variability is due to simulation error.
 The final MCMC samples will be such that this ratio for the key parameters in the model is ≤ 0.01.
- Gelman & Rubin diagnostic is based on the ratio of the pooled variance across the chains over the overall within-chain variance. Values close to 1 indicate that each of the subsets of MCMC samples is close to the target posterior distribution. A cut-off of 1.1 will be used.
- Diagnostic plots and visual inspection
 - o Trace plots (the distribution of points should not change as the chain progresses and the posterior mean and variance are relatively constant)
 - Autocorrelation plots (provide information on how slow or fast the Markov chain converges)

All the diagnostic outputs and alternative models fitted (where applicable) will be stored in the refdata folder in HARP (production) in the relevant reporting efforts.

